15.1 Data Management

Coloplast will be responsible for data management and statistical analysis. Edit checks will be created for quality control of all data collected. Data will be subjected to initial inspection for omitted data, data inconsistencies, and deviations. The resolution of any inconsistencies will be resolved through Data Query Forms (DQFs). The site will be asked to review and respond to the DQFs generated by Coloplast.

the clinical study. In the event the participant cannot read, witnessed informed consent will be allowed. The participant should be given a copy of the Consent Form.

16.1.1 Requirements

A sample informed consent document suitable for use in this study, including the elements of informed consent in conformance with 21 CFR Part 50 will be provided by the sponsor. Iterations of this document must also include the elements of informed consent in conformance with 21 CFR Part 50 and should be approved by the sponsor prior to IRB review. Participants must be presented with the most current, IRB approved version of the consent form for signature and enrollment.

16.2 Institutional Review Board

This protocol and/or other relevant documents should be submitted to the appropriate local Institutional Review Board (IRB). Written approval must be obtained before commencement of the investigation. Approval obtained from the local IRB should document the version of the protocol and consent for that is being approved.

Any amendment to the protocol that impacts the conduct of the study will also be submitted to the same IRB.

16.3 Data Protection

All information collected during the course of this investigation will be kept strictly confidential. Any information that could identify a participant will remain with the investigator where it will be archived with study documents. Participants will remain anonymous for the purposes of data analysis. Data collected for the purposes of this study should be made available for Coloplast at all monitoring visits.

Should the investigation require future review, it may be necessary to allow limited access to Coloplast and regulatory authorities for audit purposes only.

17 Publication

Coloplast will form a publication committee that includes at a minimum the Study Principal Investigator and at least one other participating investigator. The committee will develop a publication strategy in collaboration with Coloplast. The scientific validity and timing of publications will be evaluated in order to maximize the benefits derived from the publication of the clinical data of the study.

18 Records and Retention

18.1 Sponsor Responsibilities

Coloplast, the study sponsor will maintain the following records:

- All correspondence which pertains to the investigation

- Signed Investigator Agreements, financial disclosure information, and current curriculum vitae

- IRB approval correspondence

- Adverse events, deaths, and complaints

- All case report forms submitted by investigator, samples of informed consents/ applicable privacy protection authorizations, investigational plan and report of prior investigations

- Study training records for all site personnel

Monitoring reports
Study reports

18.1.1 Sponsor Reports

The following table details submission requirements for each report.

Table 4 Sponsor Reports

Report	Submit To	Description
Adverse Reaction	Investigators' IRBs and FDA, as applicable	Notification within 15 working days after the sponsor first learns of the effect.
Withdrawal of Local IRB approval	Investigators' IRBs	Notification within 5 working days.
Recall and product disposition	Investigators' IRBs, as applicable FDA/ Applicable Competent Authorities	Notification within 30 working days; will include the reasons for any request that an investigator return, repair, or otherwise dispose of any products.
Progress Reports	Investigators' IRB, as applicable	Annually
Final report	Investigators' IRB, as applicable	Coloplast will notify the investigators of the completion or termination of the investigation. Investigators will, in turn, inform their IRBs. A final report will be submitted to the investigators and IRBs within six months after completion or termination of this study.

18.12 Records Retention

The sponsor will archive and retain all remaining documents pertaining to the investigation for a minimum of 10 years.

18.2 Investigator Responsibilities

In addition to the requirements stated in the investigator agreement, the investigator is responsible for the preparation (review and signature) and retention of the records cited below. All of the records below, with the exception of case history records, should be kept in the Investigator Site File (i.e., the study binder provided to the investigator). The following records are subject to inspection and must be retained according to the agreed upon timeframe in the investigator agreement (or longer as local law or hospital administration requires) after study closure.

All substantial correspondence that pertains to the conduct of the investigation. Any correspondence describing rationale for decisions made affecting participant safety and privacy or data collection and reporting is considered substantial correspondence.

Participant's case history records including: signed informed consent/applicable privacy protection authorization form; observations of adverse events/adverse device effects; medical history; implant and follow-up data; documentation of the dates and rationale for any deviation from the protocol.

[REDACTED]

[REDACTED]

[REDACTED]

[REDACTED]

[REDACTED]	[REDACTED]	[REDACTED]
[REDACTED]	[REDACTED]	[REDACTED]

[REDACTED]

[REDACTED]

[figure not shown]
[REDACTED]

[figure not shown]
[REDACTED]

[figure not shown]
[REDACTED]

[figure not shown]
[figure not shown]
[REDACTED]

[figure not shown]
[REDACTED]

Appendix B: Patient Questionnaires

Patient Global Impression of Improvement for Urogenital Prolapse (PGI-I for Urogenital Prolapse)

Subject ID: _____ - _____

Visit Date: ____/____/____
MM/DD/YYYY

1. Check the box that best describes how your urinary tract condition is now, compared with how it was before you had the operation.

¹Very much better ²Much better ³A little better ⁴No change

⁵A little worse ⁶Much worse ⁷Very much worse

Reference:

**Pelvic Floor Distress Inventory –
Short Form 20**

Subject ID: _____ - _____
Visit Date: ____/____/____ MM/DD/YYYY

Instructions:

Please answer the questions by putting an X in the appropriate box. If you are unsure about how to answer a question, give the best answer you can. While answering these questions, please consider your symptoms over the last 3 months. CHECK ONE BOX PER QUESTION. Thank you for your help.*

1. Do you usually experience *pressure* in the lower abdomen? No Yes
If yes, how much does this bother you?
₁ Not at all ₂ Sometimes ₃ Moderately ₄ Quite a bit
◇ ◇ ◇ ◇ ◇ ◇
2. Do you usually experience *heaviness* or *dullness* in the pelvic area? No Yes
If yes, how much does this bother you?
₁ Not at all ₂ Sometimes ₃ Moderately ₄ Quite a bit
◇ ◇ ◇ ◇ ◇ ◇
3. Do you usually have a bulge or something falling out that you can see or feel in the vaginal area? No Yes
If yes, how much does this bother you?
₁ Not at all ₂ Sometimes ₃ Moderately ₄ Quite a bit
◇ ◇ ◇ ◇ ◇ ◇
4. Do you usually have to push on the vagina or around the rectum to have a complete bowel movement? No Yes
If yes, how much does this bother you?
₁ Not at all ₂ Sometimes ₃ Moderately ₄ Quite a bit
◇ ◇ ◇ ◇ ◇ ◇
5. Do you usually experience a feeling of incomplete bladder emptying? No Yes
If yes, how much does this bother you?
₁ Not at all ₂ Sometimes ₃ Moderately ₄ Quite a bit
◇ ◇ ◇ ◇ ◇ ◇
6. Do you ever have to push up on a budge in the vaginal area with your fingers to start or complete urination? No Yes
If yes, how much does this bother you?
₁ Not at all ₂ Sometimes ₃ Moderately ₄ Quite a bit

Subject ID: _____ - _____
Visit Date: ____/____/____ MM/DD/YYYY

- 14. Does a part of your bowel ever pass through the rectum and bulge outside during or after a bowel movement?
If yes, how much does this bother you?
₀ No Yes
₁ Not at all ₂ Sometimes ₃ Moderately ₄ Quite a bit
◇◇◇◇◇◇
- 15. Do you usually experience frequent urination?
If yes, how much does this bother you?
₀ No Yes
₁ Not at all ₂ Sometimes ₃ Moderately ₄ Quite a bit
◇◇◇◇◇◇
- 16. Do you usually experience urine leakage associated with a feeling of urgency, that is a strong sensation of needing to go to the bathroom?
If yes, how much does this bother you?
₀ No Yes
₁ Not at all ₂ Sometimes ₃ Moderately ₄ Quite a bit
◇◇◇◇◇◇
- 17. Do you usually experience urine leakage related to coughing, sneezing, or laughing?
If yes, how much does this bother you?
₀ No Yes
₁ Not at all ₂ Sometimes ₃ Moderately ₄ Quite a bit
◇◇◇◇◇◇
- 18. Do you usually experience small amounts of urine leakage (that is drops)?
If yes, how much does this bother you?
₀ No Yes
₁ Not at all ₂ Sometimes ₃ Moderately ₄ Quite a bit
◇◇◇◇◇◇
- 19. Do you usually experience difficulty emptying your bladder?
If yes, how much does this bother you?
₀ No Yes
₁ Not at all ₂ Sometimes ₃ Moderately ₄ Quite a bit
◇◇◇◇◇◇
- 20. Do you usually experience *pain* or *discomfort* in the lower abdomen or genital region?
If yes, how much does this bother you?
₀ No Yes
₁ Not at all ₂ Sometimes ₃ Moderately ₄ Quite a bit

Subject ID: _____
Visit Date: ____/____/____ MM/DD/YYYY

Pelvic Floor Impact Questionnaire – short form 7

Instructions: Some women find that bladder, bowel or vaginal symptoms affect their activities, relationships, and feelings. For each question, place an X in the response that best describes how much your activities, relationships, and feelings have been affected by your bladder, bowel, or vaginal symptoms or conditions over the last 3 months. Please be sure to mark an answer in **all three columns** for each question. Thank you for your cooperation.*

How do symptoms or conditions related to the following usually affect your... ↓	Bladder or urine	Bowel or rectum	Vagina or Pelvis
1. ability to do household chores (cooking, housecleaning, laundry)?	 Not at all  Somewhat  Moderately  Quite a bit	 Not at all  Somewhat  Moderately  Quite a bit	 Not at all  Somewhat  Moderately  Quite a bit
2. ability to do physical activities such as walking, swimming, or other exercise?	 Not at all  Somewhat  Moderately  Quite a bit	 Not at all  Somewhat  Moderately  Quite a bit	 Not at all  Somewhat  Moderately  Quite a bit
3. entertainment activities such as going to a movie or concert?	 Not at all  Somewhat  Moderately  Quite a bit	 Not at all  Somewhat  Moderately  Quite a bit	 Not at all  Somewhat  Moderately  Quite a bit
4. ability to travel by car or bus for a distance greater than 30 minutes away from home?	 Not at all  Somewhat  Moderately  Quite a bit	 Not at all  Somewhat  Moderately  Quite a bit	 Not at all  Somewhat  Moderately  Quite a bit
5. participating in social activities outside your home?	 Not at all  Somewhat  Moderately  Quite a bit	 Not at all  Somewhat  Moderately  Quite a bit	 Not at all  Somewhat  Moderately  Quite a bit
6. emotional health (nervousness, depression, etc.)?	 Not at all  Somewhat  Moderately  Quite a bit	 Not at all  Somewhat  Moderately  Quite a bit	 Not at all  Somewhat  Moderately  Quite a bit
7. feeling frustrated?	 Not at all  Somewhat  Moderately  Quite a bit	 Not at all  Somewhat  Moderately  Quite a bit	 Not at all  Somewhat  Moderately  Quite a bit

Subject ID: _____ - _____
Visit Date: ____/____/____ MM/DD/YYYY

Pelvic Organ Prolapse / Urinary Incontinence Sexual Function Questionnaire (PISQ-12)

Instructions: The following are a list of questions about you and your partner's sex life. All information is strictly confidential. Your confidential answers will be used only to help doctors understand what is important to patients about their sex lives. Please check the box that best answers the question for you. While answering the questions, consider your sexuality over the last 6 months. CHECK ONE BOX PER QUESTION. Thank you for your help.*

I am not sexually active or I am not comfortable answering these questions (do not answer the questions below).

1. How frequently do you feel sexual desire? This feeling may include wanting to have sex, planning to have sex, feeling frustrated due to lack of sex, etc.

Always Usually Sometimes Seldom Never

2. Do you climax (have an orgasm) when having sexual intercourse with your partner?

Always Usually Sometimes Seldom Never

3. Do you feel sexually excited (turned on) when having sexual activity with your partner?

Always Usually Sometimes Seldom Never

4. How satisfied are you with the variety of sexual activities in your current sex life?

Always Usually Sometimes Seldom Never

5. Do you feel pain during sexual intercourse?

Always Usually Sometimes Seldom Never

6. Are you incontinent of urine (leak urine) with sexual activity?

Always Usually Sometimes Seldom Never

7. Does fear of incontinence (either stool or urine) restrict your sexual activity?

Always Usually Sometimes Seldom Never

8. Do you avoid sexual intercourse because of bulging in the vagina (either bladder, rectum, or vagina falling out)?

Always Usually Sometimes Seldom Never

9. When you have sex with your partner, do you have negative emotional reactions such as fear, disgust, shame or guilt?

Always Usually Sometimes Seldom Never

Subject ID: _____ - _____
Visit Date: ____/____/____ MM/DD/YYYY

Pelvic Organ Prolapse / Urinary Incontinence Sexual Function Questionnaire (PISQ-12)

10. Does your partner have a problem with erections that affects your sexual activity?
 Always Usually Sometimes Seldom Never
11. Does your partner have a problem with premature ejaculation that affects your sexual activity?
 Always Usually Sometimes Seldom Never
12. Compared to orgasms you have had in the past, how intense are the orgasms you have had since your last study visit?
 Much less intense Less intense Same intensity More intense Much more intense

Date: ____/____/____

Name: _____

Surgical Satisfaction Questionnaire SSQ-8

Instructions: Following are a list of questions about your satisfaction with your surgery. All information is strictly confidential. Your confidential answers will be used only to help doctors understand and improve what is important to patients before, during and after surgery. Please check the box that best answers the question for you. Thank you for your help.

- 1. How satisfied are you with how your pain was controlled in the hospital after surgery?
 Very Satisfied Satisfied Neutral Unsatisfied Very unsatisfied
- 2. How satisfied are you with how your pain was controlled when you returned home after surgery?
 Very Satisfied Satisfied Neutral Unsatisfied Very unsatisfied
- 3. How satisfied are you with the amount of time it took for you to return to your daily activities, for example housework or social activities outside the home?
 Very Satisfied Satisfied Neutral Unsatisfied Very unsatisfied
- 4. How satisfied are you with the amount of time it took for you to return to work?
 Very Satisfied Satisfied Neutral Unsatisfied Very unsatisfied N/A
- 5. How satisfied are you with the amount of time it took for you to return to your normal exercise routine?
 Very Satisfied Satisfied Neutral Unsatisfied Very unsatisfied N/A
- 6. How satisfied are you with the results for your surgery?
 Very Satisfied Satisfied Neutral Unsatisfied Very unsatisfied
- 7. Looking back, if you "had to do it all over again" would you have the surgery again?
 Yes Maybe (probably yes) Unsure Don't think so Never
- 8. Would you recommend this surgery to someone else?
 Yes Maybe (probably yes) Unsure Don't think so Never

NOTES: Research Nurses Notes

Originated 08/08

Subject ID#: _____ Date: _____ Visit: (Circle) Pre-Op 1 2 3 4 5

Indicate pain on the line below, with one vertical mark
Do not write a number

Pelvic/Bladder Pain with Daily Activity

No Pain	_____	Worst Pain
---------	-------	------------

Pelvic/Bladder Pain with Sexual Activity

No Pain	_____	Worst Pain
---------	-------	------------

Comments:

To obtain "final" score use a 10-cm measurement tool/ruler, clinician can note precise VAS score to the tenths decimal place (e.g. 8.2 cm, 3.1 cm).

Final VAS score: _____ (Daily Activity); _____ (Sexual Activity)

VAS Entered into Database by/Date: _____ PI Review/Date: _____

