5.1 Primary Objective

The primary objective of this study is to evaluate efficacy of the Axis Dermis graft used for soft tissue repair, replacement, reconstruction, or augmentations in the correction of POP as assessed by POP-Q Stage improvement based upon an objective grading of prolapse of the anterior, posterior or combined anterior and posterior (assessed individually) compartment(s) compared between baseline and one year. Grading of the prolapse will be categorized as follows:

Cured: POP-Q Stage reduced to 0 or 1, or improved by 2 stages from baseline

Improved: POP-Q Stage > 1, but improved by 1 stage from baseline

Failed: POP-Q Stage stayed the same or increased in severity from baseline

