5.2 Secondary Objectives

Secondary objectives will assess POP-Q Stage and patient satisfaction at 6 weeks, 6 months, 2 years, and 3 years post implant, as follows:

Change in prolapse stage from baseline as determined objectively by POP-Q prolapse grading at 6 weeks, 6 months, 2 year, and 3 year follow-ups. Change in patient satisfaction from baseline and quality of life measured through validated questionnaires (PDFI-20 and PFIQ-7)⁶

Change in patient sexual satisfaction from baseline measured through a validated questionnaire (PISQ-12)⁷

Summary of Patient Global Impression of Improvement (PGI-I) for urogenital prolapse⁹ results

Summary of The Institute for Female Pelvic Medicine & Reconstructive Surgery Surgical Satisfaction Questionnaire (SSQ-8) results¹⁰

Change in Pelvic and Sexual Health Institute Visual Analog Scale (VAS)¹¹ results

Surgical revision rate of the index prolapse(s)

Summary of all mild, moderate, and serious product and/or procedure related adverse events

6 Study Population

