6.1 Participant Population

The study population will be adult female patients with pelvic organ prolapse, POP-Q Stage ≥ 2 that are clinically indicated for surgical intervention with Axis human tissue in the anterior, posterior or combined (anterior and posterior) compartments at the institutions designated for this study. All study candidates must be able to understand the nature of the procedure, provide written informed consent, and be available for follow-up at an approved investigational site.

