6.4 Exclusion Criteria

Patients who meet any of the following criteria are excluded from entry into the study:

1. Concurrent surgical treatment of pelvic organ prolapse using anything other than the Axis Dermis. [Note: concurrent mid-urethral sling placement for treatment of stress urinary incontinence is allowed].
2. Confirmed Stage 2 or higher prolapse as determined by POP-Q prolapse grading for a compartment that is **not** being repaired in the same procedure. (Concurrent POP-Q Stage 1 repair is at the physician's discretion.)
3. Previous pelvic organ prolapse repair using biologic, or synthetic grafts. [Note: previous mid-urethral sling for treatment of stress urinary incontinence is allowed]
4. Pregnant or a desire to become pregnant in the future.
5. Previous radiation or other treatments for cancer in the pelvic area.
6. Severe urogenital atrophy.
7. Immunosuppression and/or current systemic steroid user.
8. Any contraindication to the surgical procedure.

7 Enrollment

[figure not shown]
After it has been determined that a potential study participant meets the entrance criteria and prior to data being collected, an informed consent must be obtained. There is no formal screening process outside of standard of care procedures required to determine participant eligibility. [REDACTED]

[REDACTED] Once it is determined the participant meets all of the inclusion and none of the exclusion criteria, they are considered enrolled in the study. When they are enrolled they will receive a subject number.

8 Procedures

Clinical data will be collected at baseline, implant, 6 weeks, 6 months, 1 year, 2 years, and 3 years post-operatively. The Data Collection Schedule below provides an outline of what clinical and participant data is collected at each visit (Table 1).

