11.4 Adverse Event Review

An Independent Medical Advisor will review all Serious Adverse Events and Adverse Reactions on a periodic basis to be determined by nature and number of reported serious adverse events.

12 Withdrawal / Study Exit

In the event that a participant is unable or unwilling to continue participation in the study, notify Coloplast as soon as possible.

If a participant expresses the desire to withdraw from the study, a Withdrawal / Study Exit Case Report Form must be completed. The reason for participant withdrawal must be documented on this form.

In the case that the participant fails to comply with the follow-up schedule, the study site must make multiple attempts to contact the participant (e.g. telephone, registered mail). Each attempt to contact the participant must be documented in the participant's records. In the case that the participant is determined to be lost to follow-up, a Withdrawal / Study Exit Case Report Form must also be completed.

Participants will be considered to have completed the study after their two year follow up visit has been completed and all outstanding adverse events have been resolved or are permanently ongoing.

13 Electronic Case Report Forms (eCRFs)

The eCRFs are designed to accommodate the specific features of the study design and will be used to capture study specific data and store in a secured FDA 21 CFR 11 compliant database. Training will be provided for all study personnel entering data into the electronic database prior to being given access to the database.

Sites will enter data on eCRFs using Electronic Data Capture (EDC). All visit information will be captured in the EDC system. [REDACTED]

[REDACTED] The data from the questionnaires will be entered by the site into the EDC system after completion.

The investigator or relevant staff member who has signed the eCRF Authorization Log may complete the eCRF. The investigator will review all eCRFs for completeness and electronically sign the forms.

14 Statistical Methods

The key endpoints are specified below:

Efficacy: Efficacy metrics will include objective POP-Q prolapse grading as well as patient satisfaction (as measured by subject questionnaires) post-operatively at [REDACTED]

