14.2 Statistical Analysis

[REDACTED]

[REDACTED] Results will be compared to competitive products from the available literature.

The primary analyses will include all subjects enrolled and followed. Additional analyses will be conducted where results are tabulated separately for subjects who require a revision procedure in one or both compartments and receive a product other than Axis Dermis and those who do not receive any additional product other than Axis Dermis during study follow-up.

15 Data Quality Assurance

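### The PGI-I is listed as a prolapse outcome but asks only about the urinary tract, and PISQ-12 item 12 has no reference point at baseline (minor; secondary outcomes only)

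*Combined protocol and SAP*

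**What the plan says.** **PGI-I.** Section 5.2 names as a secondary objective "Summary of Patient Global Impression of Improvement (PGI-I) for urogenital prolapse". The form in Appendix B carries the same prolapse label in its title. It has one numbered item with seven response boxes: "Check the box that best describes how your urinary tract condition is now, compared with how it was before you had the operation". The item itself does not mention prolapse.

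Section 6.1 takes women "clinically indicated for surgical intervention with Axis human tissue in the anterior, posterior or combined (anterior and posterior) compartments". Section 2 describes anterior prolapse through the bladder and posterior prolapse through the rectum. The note to exclusion 1 in section 6.4 says that "concurrent mid-urethral sling placement for treatment of stress urinary incontinence is allowed".

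**PISQ-12.** Section 8.2 collects this form at baseline in sexually active women, and section 5.2 analyses it as change from baseline. The form's instructions in Appendix B set a six-month period for the questions. Item 12, on orgasm intensity, instead asks about the time since the previous study visit. The visit schedule in section 1 begins with baseline, and section 7 requires no formal screening step beyond usual care.

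**Use.** Section 14 counts patient questionnaires among the efficacy metrics. Section 14.2 states, after redacted text, "Results will be compared to competitive products from the available literature".

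**The concern.** A single-item global measure reports whatever its one question asks. Here the question concerns the urinary tract, while the objective and the form's title concern prolapse. If the plan is followed as printed, a urinary answer will be summarised as prolapse improvement. The study is single-arm, so no control group answers the same question under the same conditions, and a reader of the summary has no way to see the mismatch.

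For PISQ-12, a change score needs each item to mean the same thing at baseline and at follow-up. Item 12 has no defined period at baseline under its own words, and its period at follow-up varies from visit to visit.

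**Working it through.** The plan states no figure to reproduce on this point. The check is mainly a comparison of texts, with two short calculations.

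**1. What the PGI-I item can pick up.** The inputs are the item (Appendix B), the organ definitions (section 2), the eligible repairs (section 6.1) and the sling note (section 6.4).

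| Woman | Organ in the repaired prolapse | What a truthful answer may reflect |
|---|---|---|
| Anterior repair, no sling | Bladder | Overlaps with the repair, though the item does not ask about prolapse |
| Posterior-only repair, no sling | Rectum | Possibly no change, even after a successful repair |
| Any repair with a sling | Bladder, rectum or both | Possibly marked improvement from the sling, whatever the graft did |

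The second row can understate the repair and the third can overstate it. The net direction depends on how many women fall in each row, and the documents do not give those numbers. With one item on the form, no other item can offset the error.

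**2. What else covers the gap.**
- The primary endpoint grades prolapse by compartment: "combined anterior and posterior (assessed individually) compartment(s) compared between baseline and one year".
- PFDI-20 item 3 asks directly about the bulge: "Do you usually have a bulge or something falling out that you can see or feel in the vaginal area". Item 4 asks about manual help with bowel movements.
- PFIQ-7 has separate columns for bladder, bowel and vagina or pelvis.
- SSQ-8 items 6 to 8 ask about satisfaction with the surgical result, willingness to have the operation again, and recommending it. None of these is specific to the urinary tract.

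Patient-reported information on posterior repairs is therefore collected elsewhere. What is wrong is the label on the PGI-I result.

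**3. PISQ-12 item 12.** At baseline no earlier study visit is listed, so the item's period is undefined. At follow-up, take nominal visits at weeks 6, 26, 52, 104 and 156, with implant at week 0 as the preceding visit listed in section 1:

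- 6 − 0 = 6 weeks
- 26 − 6 = 20 weeks
- 52 − 26 = 26 weeks
- 104 − 52 = 52 weeks
- 156 − 104 = 52 weeks

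The form's instructions give about 26 weeks throughout, so item and instructions agree only at the one-year visit. The share of the form is 1/12 = 8.3% of items. The scoring is not visible. If the five boxes are coded 0 to 4 (an assumption), item 12 carries at most 4 of 12 × 4 = 48 points, also 8.3%.

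**4. Precision of a PGI-I table by compartment.** Section 14.1 expects 60 to 85 evaluable subjects at month 12. The split by compartment is not given. Purely as an illustration, three equal groups would hold 60/3 = 20 to 85/3 ≈ 28 women. At an observed 50%, the Wilson 95% half-width is z / (2√(n + z²)) with z = 1.96:

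- n = 28: 1.96 / (2√31.84) = 0.174
- n = 20: 1.96 / (2√23.84) = 0.201
- n = 10, for a smaller group: 1.96 / (2√13.84) = 0.263

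Such intervals are wide, about 17 to 26 percentage points either side.

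**The case against.** The strongest reply on the PGI-I is that the form cites a validation paper for this named instrument. If the printed item is the published wording, the sponsor is using the instrument as issued. That stands in part: the source is not in the documents, so no transcription error is shown. It does not settle the matter, because a faithful copy would still not make a urinary question measure the repair of a rectocele.

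For PISQ-12, the six-month instruction gives a woman something to answer by at baseline, and only one item is involved. Both points stand and are why the effect is small. The item and the instruction still disagree, and she may follow either.

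Much of the relevant text is also redacted or not visible: the data collection schedule, the follow-up visit content, the start of section 14.2 and the text after the screening sentence in section 7. Tabulation by compartment or questionnaire scoring may be specified there, and a separate baseline PISQ-12 cannot be fully excluded, though nothing visible points to one. This limits confidence. It does not alter the printed forms.

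Finally, section 14.1 says there are no predefined hypotheses, and the PGI-I is only to be summarised. That is a fair argument for treating the point as minor.

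**Conclusion.** The concern holds as a minor point on two secondary questionnaire outcomes. The PGI-I result, as printed, would carry a prolapse label for a urinary question, which matters most for posterior-only repairs and women with a sling. Its size cannot be computed from the documents. Item 12 affects 1 of 12 PISQ-12 items.

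Four stronger readings are tempting but not supported:

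- *The validated instruments were altered.* The source forms are not in the documents.
- *The product comparison rests on a mislabelled PGI-I.* The sentence on the literature follows a redaction, and nothing visible says which results are compared.
- *The PISQ-12 change score is unusable or needs rescoring.* One item with a six-month fallback on the same form does not show that.
- *Answers at six weeks largely describe the time before surgery.* For item 12, section 1 lists implant as a visit, so its own look-back is about six weeks. For the other recall forms, the schedule showing which are given at that visit is not visible, and any effect on the scores is unknown.

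The efficacy conclusion based on POP-Q is untouched.

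**What to change.** **PGI-I.**
- Check the item against the cited prolapse version. If it differs, replace it with that wording and do not pool answers from the two versions.
- Describe any answers collected with the urinary wording as improvement in urinary tract condition, not as prolapse improvement.
- In either case, tabulate PGI-I by repaired compartment and, separately, by concurrent sling. Give counts only where groups are small.

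**PISQ-12 item 12.** Check it against the source form and make the printed item agree with the form's stated recall period at every visit. Make the change on the form itself: section 8.4 allows questionnaires to be mailed when a woman cannot be seen, so an instruction to sites may not reach her.

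**Cost.** Two checks against source forms, one wording correction or two, and two short tables. The compartment is needed for the primary endpoint anyway. Sling status should come from the procedure records, but the content of that form is not visible and should be confirmed. The downsides are two PGI-I versions that cannot be combined if the wording changes mid-study, and subgroup intervals wide enough that the tables are descriptive only. After correction, item 12 shares whatever limits the six-month period has for the other items.
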